5.7.3. Analysis of Vital Signs

Vital signs (temperature, pulse, blood pressure, and respiration rate) will be summarized by baseline and change from baseline to each scheduled assessment time with descriptive statistics.

5.7.4. Analysis of 12-Lead ECG

ECG parameters will be summarized by Baseline and change from Baseline to each scheduled assessment time with descriptive statistics.

ECG status (ie, normal, abnormal, not clinically significant, and abnormal clinically significant) will be reported. Shift tables from baseline to worst post-baseline findings (normal, abnormal not clinically significant, and abnormal clinically significant) during on-treatment period will be generated.

5.7.5. Physical Exams

Number and proportion of patients with new or worsened physical exam abnormalities during on-treatment period will be summarized.

5.8. Analysis of Anti-Drug Antibody Data

Potential association between immunogenicity variables and safety or efficacy may be explored, as appropriate.

5.9. Analysis of Exploratory Biomarker Data

Biomarker data will be analyzed using standard scientific methods and summarized by descriptive statistics and plot. Correlative analysis with clinical response may be performed using correlation coefficient, box plot and scatter plot, and basic regression models. Both comparative analysis and correlative analysis will be exploratory in nature and will be described in a separate report.

6. DATA CONVENTIONS

The following analysis conventions will be used in the statistical analysis.

6.1. Definition of Baseline for Efficacy/Safety Variables

Unless otherwise specified, the Baseline assessment for all measurements will be the latest available valid measurement taken prior to the administration of investigational product.

6.2. Definition of Study Day

Study day 1 is the day of patient receiving first dose of cemiplimab. Study day -1 is the day before patient receiving first dose of cemiplimab. There is no Day 0.

For events prior to the first day a patient receiving cemiplimab treatment, the study day is defined as the date of event - first dose of cemiplimab; for events on or after the first dose of cemiplimab, the study day is defined as date of event - date of the first dose of cemiplimab +1.

6.3. Data Handling Convention for Missing Data

No missing data imputation is planned in this study unless specified otherwise.

For categorical variables, patients with missing data are not included in calculations of percentages unless otherwise specified. When relevant, the number of patients with missing data is presented.

Medication missing/partial dates

To determine whether a medication is prior, concomitant or post-treatment medication, the missing medication start date is estimated as early as possible up to date of the first study treatment, and the missing medication end date is estimated as late as possible. If the medication start date is missing, the onset day will not be imputed in medication listings.

Date of first / last study treatment

Date of first infusion is the first non-missing start date of dosing filled in the CRF “Investigational Product” module.

AE suspected to be caused by cemiplimab

If AE suspected to be caused by cemiplimab is missing, the AE relationship will be imputed as related.

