11.2. Justification of Sample Size

Seventy-two (72) patients will be required to provide 90% power to reject a null hypothesis of a pCR rate of 25% at a 2-sided significance level of 0.05 if the true pCR rate is 44%.

The sample size will be further increased by 5% to account for patients who prematurely withdraw from the study. Hence, the total sample size will be approximately 76 patients. Patients who discontinue treatment early and/or withdraw from the study will not be replaced. Results will be analyzed according to intention-to-treat. The 95% binomial exact confidence intervals for observed pCR with 76 patients is provided in [Table 6](#).

The non-clinically meaningful pCR rate of 25% will be excluded using the lower limit of 95% exact CI if the observed pCR rate is 36.8% or more.

Table 6: The 95% Binomial Exact Confidence Intervals for Observed pCR with a Sample Size of 76 Patients

Number of pCR patients	Observed pCR rate	95%CI – lower	95% CI – upper
23	0.303	0.202	0.419
24	0.316	0.214	0.433
25	0.329	0.225	0.446
26	0.342	0.237	0.460
27	0.355	0.249	0.473
28	0.368	0.261	0.487
29	0.382	0.272	0.500
30	0.395	0.284	0.514
31	0.408	0.296	0.527
32	0.421	0.309	0.540
33	0.434	0.321	0.553

To ensure meaningful representation of stage III/IV (M0) patients, enrollment of stage II patients will be capped at 25 patients.

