1.2.4. Modifications from the Statistical Section in the Final Protocol

- The full analysis set (FAS) includes enrolled patients who received at least one dose of cemiplimab.
- Subgroup efficacy analysis was removed.

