2.2. Sample Size and Power Considerations

Seventy-two (72) patients will be required to provide 90% power to reject a null hypothesis of a pCR rate of 25% at a 2-sided significance level of 0.05 if the true pCR rate is 44%.

The sample size will be further increased by 5% to account for patients who prematurely withdraw from the study. Hence, the total sample size will be approximately 76 patients. Patients who discontinue treatment early and/or withdraw from the study will not be replaced. The 95% binomial exact confidence intervals for observed pCR with 76 patients is provided in [Table 1](#).

The non-clinically meaningful pCR rate of 25% will be excluded using the lower limit of 95% exact CI if the observed pCR rate is 36.8% or more.

Table 1: The 95% Binomial Exact Confidence Intervals for Observed pCR with a Sample Size of 76 Patients

Number of pCR patients	Observed pCR rate	95% CI – lower	95% CI – upper
23	0.303	0.202	0.419
24	0.316	0.214	0.433
25	0.329	0.225	0.446
26	0.342	0.237	0.460
27	0.355	0.249	0.473
28	0.368	0.261	0.487
29	0.382	0.272	0.500
30	0.395	0.284	0.514
31	0.408	0.296	0.527

Number of pCR patients	Observed pCR rate	95%CI – lower	95% CI – upper
32	0.421	0.309	0.540
33	0.434	0.321	0.553

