3.1. The Full Analysis Set (FAS)

The full analysis set (FAS) will include all enrolled patients who have received at least one dose of cemiplimab. Efficacy endpoints will be analyzed using the FAS.

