4.4. Efficacy Variable

4.4.1. Primary Efficacy Variable

The primary objective of the study is to evaluate the efficacy of neoadjuvant cemiplimab as measured by pathologic complete response (pCR) rate per independent central pathology review. Pathologic complete response (pCR) is defined as absence of viable cancer cells in the surgical pathology sample.

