5.6. Analyses of Efficacy Variables

The analysis of efficacy data will be performed based on the FAS, as defined in Section 3.1.

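### The SAP's missing-data default, read literally, drops dosed patients without a surgical specimen from the pCR and mPR denominators, and nothing says it does not apply

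*SAP*

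**What the plan says.** SAP 6.3 gives two defaults. The first is "No missing data imputation is planned in this study unless specified otherwise". The second is "For categorical variables, patients with missing data are not included in calculations of percentages unless otherwise specified".

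The primary variable needs tissue: "Pathologic complete response (pCR) is defined as absence of viable cancer cells in the surgical pathology sample" (SAP 4.4.1). mPR is likewise defined on the surgical sample (SAP 4.4.2).

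Other passages point to a denominator of all dosed patients:

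- Protocol 11.2, and the synopsis: "Results will be analyzed according to intention-to-treat".
- SAP 3.1: "Efficacy endpoints will be analyzed using the FAS". SAP 5.6 repeats it: "The analysis of efficacy data will be performed based on the FAS, as defined in Section 3.1".
- SAP 2.2: 25% is excluded "if the observed pCR rate is 36.8% or more". That figure is 28/76, and the accompanying table of intervals is built on 76.
- SAP 1.2.4 lists two changes from the protocol. One is "The full analysis set (FAS) includes enrolled patients who received at least one dose of cemiplimab"; the other is the removal of subgroup efficacy analysis. A denominator restricted to patients with a specimen is not listed.

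SAP 5.6.1 and 5.6.2 specify Clopper-Pearson intervals for pCR and mPR but do not say how to classify a dosed patient with no specimen.

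**The concern.** Patients without a specimen are foreseen. SAP 5 times the primary analysis to allow for patients who are no longer surgical candidates. The event-free survival (EFS) definition in SAP 4.4.2 includes progression that rules out surgery. Protocol 9.1.5.1 makes surgery after early discontinuation conditional on clinical appropriateness. Under 6.3 as written, a programmer could set pCR to missing for these patients and compute the rate over the rest, while still describing the analysis as run on the FAS.

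The SAP writes rules of this kind elsewhere. SAP 4.4.2 says how to censor EFS when there is no evaluable post-baseline assessment, and disease-free survival when there is no assessment after surgery. SAP 6.3 itself imputes missing causality as related. For pCR and mPR there is no counterpart.

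The trial's claim rests on one proportion compared with a fixed 25%. Leaving out a patient who would otherwise count as non-pCR can only raise the rate and its lower limit. The denominator should therefore be settled before data are seen.

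**Working it through.** **Inputs.** Null rate 25%, alternative 44%, two-sided 0.05, 90% power, 72 patients raised by 5% to about 76, success at 36.8% or more (Protocol 11.2, SAP 2.2). All 76 are taken as dosed. The number without a specimen, m, is not in the documents and is varied as an assumption.

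**Reproducing the plan's figures.** With the variance taken at the alternative, n = (1.960 + 1.282)² × 0.44 × 0.56 / 0.19² = 71.7, so 72. At n = 76 the Clopper-Pearson lower limit is 24.9% for 27 pCRs and 26.1% for 28, so 28/76 = 36.8% is the first success, as the SAP states. Its exact upper-tail error at 25% is 1.5%.

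**Smallest number of pCRs that excludes 25%, by denominator.**

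| Missing (m) | n = 76 − m | pCRs needed |
|---|---|---|
| 0 | 76 | 28 |
| 1–3 | 75–73 | 27 |
| 4–7 | 72–69 | 26 |

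**Same data, two denominators (lower limits).**

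- 27 pCRs: 27/76 gives 24.9% (fails); 27/75 gives 25.2% (succeeds). One exclusion is enough.
- 26 pCRs: 26/76 gives 23.7% and 26/73 gives 24.7% (both fail); 26/72 gives 25.1% (succeeds). Four exclusions are needed, which is the gap between 72 and 76.

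**Upper-tail error at a true all-patient rate of 25%, all missing patients non-pCR.** The rate among patients with specimens is 0.25 × 76/(76 − m), so the pCR count is Binomial(76 − m, 19/(76 − m)). It is compared with the smaller count (exclusion) or with 28 (full denominator).

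| m | Rate among specimens | Exclusion | Full denominator |
|---|---|---|---|
| 1 | 25.3% | 2.63% | 1.44% |
| 3 | 26.0% | 2.56% | 1.40% |
| 4 | 26.4% | 4.43% | 1.38% |
| 7 | 27.5% | 4.29% | 1.31% |

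**Relaxing the assumption that all missing are non-pCR.** With m = 4 and a share f of the missing being non-pCR, the rate among specimens is (19 − 4(1 − f))/72.

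- f = 0.9: 18.6/72 = 25.8%, error 3.5%.
- f = 0.8: 18.2/72 = 25.3%, error 2.7%.
- Missingness unrelated to response, Binomial(76 − m, 0.25): 1.3% to 2.4% for m = 1 to 7, below nominal throughout.

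**At a true all-patient rate of 44%, all missing non-pCR.** The probability that the two denominators give different conclusions is 3.1% at m = 1, 3.0% at m = 3, 5.0% at m = 4 and 4.9% at m = 7.

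**The case against.** The strongest reply is that 6.3 carries its own exception and that the FAS and intention-to-treat statements satisfy it. The SAP restricts to available data explicitly where it wants to: the ADA set requires a non-missing result and the biomarker set requires baseline data, whereas the FAS has no specimen requirement. A patient who never reaches surgery has not attained pCR, so arguably nothing is missing. The rest of 6.3 deals with medication dates, infusion dates and causality, and reads as a tabulation convention. Censoring rules exist for EFS because Kaplan-Meier estimation cannot run without them, so their presence says little about pCR.

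Most of this stands as an argument about what the authors probably intended: the full denominator is the better reading. It does not settle the text. The FAS names a set of patients, and 6.3 can operate inside any set. Intention-to-treat is a principle stated in the protocol; SAP 2.2 repeats the surrounding text without it. No sentence classifies the patient without a specimen.

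The separate pathology charter may deal with unevaluable specimens. It covers assessment of the surgical sample, so it is less likely to deal with patients who have none, though it was not available to check.

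The objection on size also has force. Patients who stop for progression or toxicity are generally still sent to surgery (Protocol 8.3.5, 9.1.5.1), and all 20 pilot patients were resected, although after two doses rather than up to four (Protocol 3.2.2).

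**Conclusion.** The concern holds in its conditional form. Applied literally to pCR and mPR, SAP 6.3 contradicts the intention-to-treat statement, the FAS analysis and the 28/76 threshold, and no passage rules that application out. It does not follow that the sponsor would drop these patients.

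The effect is modest but can be decisive near the threshold, where one excluded patient reverses the conclusion at 27 pCRs. With one to three missing there is essentially no inflation above 2.5%. With four to seven missing, all non-pCR, error reaches 4.3–4.4%; it falls quickly as that assumption is relaxed and disappears if missingness is unrelated to response. These figures assume 76 dosed patients and a fixed number missing.

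ORR is less exposed, because RECIST has an inevaluable category that is neither CR nor PR, but patients with no post-baseline scan are not addressed. This should be fixed before database lock.

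**What to change.** Add to SAP 5.6.1 and 5.6.2 wording such as:

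> The denominator for pCR and mPR is all FAS patients. FAS patients with no surgery or no evaluable specimen are counted as non-responders; the missing-data convention in 6.3 does not apply.

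For consistency, state that patients who are inevaluable or have no post-baseline scan count as non-responders for ORR. Report the rate among patients with an evaluable specimen as a sensitivity analysis.

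The cost is one or two sentences and possibly a slightly lower point estimate. The effect on power depends on what the 44% describes, which the documents do not say. If it is the rate among patients with a specimen and four of 76 have none, power is P(X ≥ 28 | 72, 0.44) = 83.9% on the full denominator, against P(X ≥ 26 | 72, 0.44) = 93.0% with exclusion. If it is already the all-patient rate, the 28/76 rule has about 91.6% power. If the full denominator was intended all along, the added sentences cost no power.

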6.4. Unscheduled Assessments

Unscheduled visit measurements may be used to provide a measurement for a baseline or endpoint value if appropriate according to their definition. The measurements may also be used to determine abnormal laboratory or ECG values.

The determination of baselines and worst post-baseline values for both efficacy and safety variables will be based on scheduled available assessments and unscheduled available assessments.

Extra assessments (laboratory data or vital signs associated with non-protocol clinical visits or obtained in the course of investigating or managing adverse events) will be included in listings, but not by visit summaries except for the endpoint determination. If more than one laboratory value is available for a given visit, the first observation will be used in summaries and all observations will be presented in listings.

7. INTERIM ANALYSIS

No interim analysis is planned for the primary endpoint.

8. SOFTWARE

All analyses will be done using SAS Version 9.4 or above.

